- ^c ECGs will be collected and read locally. All ECGs must be performed after the participant has been in a supine position for at least 5 minutes.
- ^d Chemistry, hematology, coagulation, and urinalysis at Screening and at all additional timepoints. Myoglobin (urinalysis) and serum creatine kinase (biochemistry) at Screening and at additional timepoints at the discretion of the investigator. A serum sample for blood alcohol level will be collected at Screening and all additional timepoints. HgA1c will be collected at Week 12 and Week 24.
- [REDACTED]
- ^f If a participant experiences AEs at any time during the Treatment Period that are considered by the investigator to be related to the IP and not tolerable, the investigator may reduce the dose of IP in 15 mg decrements. Self-administration of IP will be interrupted for 3 to 8 days before the initiation of the reduced dose.
- ^g Participants will self-administer on an outpatient basis a single dose of SAGE-324 once daily in the evening before bed, with a snack if bedtime is not within 2 hours of the evening meal.

Table 4: Schedule of Assessments: Month 9 to Follow-up Period

Assessment	Treatment Period						Follow-up Period	
	Month 9	Month 12	Month 15	Month 18	Month 21	Month 24 to Month 60 (Every 3 Months)	EOT 3 (± 3) days after last dose of SAGE-324	EOS 14 (± 3) days after last dose of SAGE-324
Study Month								
Window (Weeks)	± 2							
Pregnancy test	X (urine; WOCBP only)	X (urine; WOCBP only)	X (urine; WOCBP only)	X (urine; WOCBP only)				
Complete physical examination, including neurological examination including MSE ^a	X	X	X	X	X	X	X	X
Body weight ^b		X				X		X
Vital signs ^c	X	X	X	X	X	X	X	X
12-Lead ECG ^d	X	X	X	X	X	X	X	X
Chemistry/hematology/ coagulation/urinalysis ^e	X	X	X	X	X	X	X	X
C-SSRS ("Since Last Visit" form)	X	X	X	X	X	X	X	X
ESS	X	X	X	X	X	X	X	X
PWC-20							X	X
Dispense SAGE-324 ^f	X	X	X	X	X	X		

Assessment	Treatment Period						Follow-up Period	
	Month 9	Month 12	Month 15	Month 18	Month 21	Month 24 to Month 60 (Every 3 Months)	EOT 3 (± 3) days after last dose of SAGE-324	EOS 14 (± 3) days after last dose of SAGE-324
Study Month								
Window (Weeks)	± 2	± 2	± 2	± 2	± 2	± 2		
SAGE-324 accountability	X	X	X	X	X	X	X	X
SAGE-324 administration ^h	Administered once daily before bed							
AEs/SAEs	X							
Concomitant medication	X							

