7. INVESTIGATIONAL PLAN

7.1. Overall Study Design

This is an open-label study to evaluate the long-term safety and tolerability of SAGE-324 in participants with ET who have completed the planned End of Treatment (EOT) Visit and who were not early terminated during the planned Treatment Period in another SAGE-324 study.

The study design is presented in Figure 2.

Figure 2: Study Design

This study includes a Screening Period of up to 28 days, a Treatment Period with weekly outpatient visits for the first 8 weeks, outpatient visits on Weeks 10, 12, 16, 20, and 24, and quarterly outpatient visits thereafter to the end of dosing, and a 14-day Follow-up Period. After providing informed consent, participants will undergo screening assessments as outlined in [Table 2](#) to determine eligibility.

Screening Period:

The Screening Period begins with the signing of the informed consent form (ICF). Eligible participants will complete additional eligibility and baseline assessments, as specified in the Schedule of Assessments ([Table 2](#)).

At the discretion of the investigator, clinical laboratory assessments from a completed SAGE-324 study may be used to determine eligibility for this study if taken within 28 days of Day 1.

Open-label Treatment Period:

Starting on Day 1, participants will self-administer on an outpatient basis a single dose of SAGE-324 once daily in the evening before bed, with a snack if bedtime is not within 2 hours of the evening meal. Guidance on suitable snacks will be provided.

During the Treatment Period, participants will return to the study center for safety, tolerability, [REDACTED] as specified in [Table 2](#), [Table 3](#), and [Table 4](#). In addition, safety phone call study visits will be conducted as deemed appropriate by the investigator to review the current status of the participant. Participants will be trained on the use of software applications and devices necessary to complete questionnaires and/or self-rated study assessments.

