Participants should gain experience with the study drug to see how it affects them before engaging in potentially hazardous activities requiring mental alertness, such as driving. If participants experience any sleepiness, dizziness, or feelings of relaxation, or have other sedative effects, they should not engage in potentially hazardous activities requiring mental alertness, such as driving, until any sleepiness/sedative effects from the study drug have dissipated. This is important because study participants may not be able to judge how these sedative effects will affect their ability to perform potentially hazardous activities requiring mental alertness, including driving.

The Treatment Period will continue for as long as the participant continues to self-administer SAGE-324 or until marketing authorization, projected to be up to approximately 5 years.

Follow-Up Period:

Follow-up visits will be conducted on an outpatient basis when participants have completed the Treatment Period. Participants will continue to complete questionnaires as indicated in [Table 4](#) and will return to the clinic 3 (± 3) days after the last dose of SAGE-324 for safety, tolerability, [REDACTED] at the End of Treatment (EOT) Visit. Participants will return to the study center for an End of Study (EOS) Visit, 14 (± 3) days after the last dose of SAGE-324.

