12.1.7. Columbia-Suicide Severity Rating Scale (C-SSRS)

Suicidality will be monitored during the study using the C-SSRS ([Posner 2011](#)). This scale consists of a baseline evaluation that assesses the lifetime experience of the participant with suicidal ideation and behavior, and a post-baseline evaluation that focuses on suicidality since the last study visit. The C-SSRS includes 'yes' or 'no' responses for assessment of suicidal ideation and behavior as well as numeric ratings for severity of ideation, if present (from 1 to 5, with 5 being the most severe).

The "Baseline/Screening" C-SSRS form will be completed at Screening (lifetime history and past 24 months). The "Since Last Visit" C-SSRS form will be completed at all subsequent time points outlined in the Schedules of Assessments ([Table 2](#), [Table 3](#), and [Table 4](#)).

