8.4.6. Columbia Suicide Severity Rating Scale (C-SSRS)

All by-visit C-SSRS summary tables will present results for Safety Set participants overall, and also by dose level received prior to the given visit. For summarization of incidence data any time post-baseline, Safety Set participant data will be summarized according to the dose received immediately prior to the evaluation (thus, a participant may contribute data under more than one dose if a criterion was met post-baseline while taking different doses).

Suicidality data collected on the C-SSRS is collected during the clinic visits at Screening and post-baseline visits. The C-SSRS includes ‘yes’ or ‘no’ responses for assessment of suicidal ideation with numeric rating for the severity (from 1 to 5 with 5 being the most severe) and behavior (from 6 to 10 with 10 being most severe). The “Baseline/Screening” C-SSRS form will be completed at screening (lifetime history and past 24 months). The “Since Last Visit” C-SSRS form will be completed at all subsequent visits.

The categorical outcomes of C-SSRS with binary response (“Yes”/ “No”) include:

Suicidal ideation with 5 being the worst:

- 1: wish to be dead

- 2: non-specific active suicidal thoughts
- 3: active suicidal ideation with any methods (not plan) without intent to act
- 4: active suicidal ideation with some intent to act, without specific plan
- 5: active suicidal ideation with specific plan and intent

Suicidal behavior with 10 being the worst:

- 6: preparatory acts or behavior
- 7: aborted attempt
- 8: interrupted attempt
- 9: actual attempt
- 10: completed suicide

Suicidal behavior is considered worse than suicidal ideation. The participant's non-suicidal self-injurious behavior is also assessed separately as part of C-SSRS:

- 11: self-injurious behavior without suicidal intent

Baseline for each question is defined as the worst of the assessments done before the first dose of IP, excluding the lifetime version. This will typically include the 'past 24-month' version from screening and 'since last visit' version from Day 1, as well as any unscheduled visits done before the first dose of IP; any 'Yes' response will make the baseline value as 'Yes'.

The number and percentage of participants with at least one response of 'Yes' to any C-SSRS suicidal ideation or suicidal behavior item, as well as for participant's non-suicidal self-injurious behavior, will be summarized by visit.

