Change from baseline for C-SSRS will be assessed using shift tables. Summary of shift from baseline in C-SSRS suicidal ideation and suicidal behavior will be presented for the categories "no suicidal ideation/behavior", "suicidal ideation", and "suicidal behavior" for each scheduled assessment time point. If the answer to all 5 assessments in suicidal ideation and all 5 assessments in suicidal behavior is 'No', then the category for the table is considered as 'No suicidal ideation/behavior'. If any of the assessments in suicidal behavior are 'Yes', the category is considered as 'Suicidal behavior'. If any of the assessments in suicidal ideation are 'Yes' but all assessments in suicidal behavior are 'No', the category is considered as 'Suicidal ideation'.

In addition, a summary of shift in suicidal ideation from baseline maximum rank score for any time post-baseline maximum rank score will be presented. Maximum score 0 refers to all 'No' for all assessments in the desired period for all 5 questions on suicidal ideation.

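### C-SSRS results by visit and by dose rest on look-backs of 1 to about 15 weeks, so they are not comparable without a person-time rate

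*SAP*

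**What the plan says.** Protocol 12.1.7 uses a lifetime and 24-month form at Screening, then "a post-baseline evaluation that focuses on suicidality since the last study visit". The recall period of each later form is therefore the gap between visits.

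Protocol 7.1 sets those gaps: "weekly outpatient visits for the first 8 weeks, outpatient visits on Weeks 10, 12, 16, 20, and 24", then "quarterly outpatient visits thereafter to the end of dosing, and a 14-day Follow-up Period". Participants "will return to the clinic 3 (± 3) days after the last dose of SAGE-324" for the EOT visit, and attend EOS 14 (± 3) days after the last dose. The schedules of assessments (Protocol Tables 2 to 4) mark the since-last-visit form at every visit from Day 1 on, including EOT and EOS.

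SAP 8.4.6 gives counts and percentages of any Yes on an ideation or behavior item, and "non-suicidal self-injurious behavior, will be summarized by visit". It adds a shift table (none, ideation, behavior) "for each scheduled assessment time point". Both are presented overall and by the dose received before the visit (Tables 14.3.4.7.1 and 14.3.4.7.2). One cumulative display is named, Table 14.3.4.7.3: the shift in maximum ideation score at any time post-baseline. The visible text has no person-time denominator and no note on the period covered. Protocol 13.7.7 asks for C-SSRS data to be listed and summarized by visit.

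**The concern.** A percentage from a form covering one week and a percentage from a form covering three months measure different things. For the same underlying risk, the longer look-back cannot give the lower chance of a Yes. Placed side by side in one table, such figures can suggest a change in suicidality that comes from the visit calendar.

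C-SSRS response is a secondary endpoint (SAP 4.2) and the study has no control arm, so readers will look at patterns over visits and doses. Two misreadings are possible. A step up when visits become quarterly can look like late-emerging suicidality. A higher percentage at 60 mg than at 15 to 45 mg can look like a dose relationship. In addition, for participants who stop after long treatment, the short EOT-to-EOS form sits next to quarterly forms and can make the period off drug look quieter than it is.

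**Working it through.** The documents give no C-SSRS rate, so there is no figure of the plan's own to reproduce. The look-backs come from the schedule; the rates below are assumptions.

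**1. Look-backs.** Taking a month as 365.25/12 = 30.44 days:
- Week 24 to Month 9: 273.9 − 168 = 105.9 days = 15.1 weeks (12.1 to 18.1 with the visit windows).
- Later quarters: 91.3 days = 13.0 weeks (9.0 to 17.0 with the windows).
- EOT to EOS: 14 − 3 = 11 days. EOT falls 0 to 6 days and EOS 11 to 17 days after the last dose, so the range is 5 to 17 days.

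With 28-day months, Month 9 and the later quarters are both 12.0 weeks.

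**2. Constant risk, short episodes.** Per-visit percentage = 1 − exp(−rate × look-back). At an assumed 2 per 100 person-years, with all 750 planned participants (SAP 5.2) attending:

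| Visit | Look-back (weeks) | Percent with a Yes | Expected number of 750 |
|---|---|---|---|
| Days 8 to 57 | 1.0 | 0.038 | 0.29 |
| Weeks 10, 12 | 2.0 | 0.077 | 0.57 |
| Weeks 16, 20, 24 | 4.0 | 0.153 | 1.15 |
| Month 9 | 15.1 | 0.578 | 4.34 |
| Later quarters | 13.0 | 0.499 | 3.74 |
| EOS | 1.6 | 0.060 | 0.45 |

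Unrounded, Month 9 is 15.1 times and a later quarter 13.0 times the weekly value. EOS is 0.12 of a quarterly value. For rates from 0.5 to 10 per 100 person-years the two ratios stay near 15 and 13.

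**3. Persistent episodes.** Let episodes last D weeks on average and start at a rate r per week. The proportion in an episode at any time is π = rD/(1 + rD), and the per-visit percentage is π + (1 − π)(1 − exp(−r × look-back)). At the same 2 per 100 person-years:

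| Mean episode (weeks) | Weekly % | Quarterly % | Quarterly / weekly | EOS / quarterly |
|---|---|---|---|---|
| 4 | 0.191 | 0.651 | 3.4 | 0.33 |
| 13 | 0.534 | 0.992 | 1.9 | 0.56 |
| 26 | 1.025 | 1.481 | 1.4 | 0.71 |
| 52 | 1.992 | 2.443 | 1.2 | 0.82 |

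The direction holds; the size depends heavily on persistence.

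**4. Susceptible participants leaving after a first Yes.** Suppose 3% are susceptible. With a hazard of 1 per year among them, the percentage is 0.057 at Day 8, 0.482 at Month 9 and 0.006 at Month 60. With a hazard of 10 per year it is 0.523 at Day 8 and 0.029 at Month 9. The observed pattern can therefore fall despite the look-back effect.

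**5. Dose.** On the planned titration (Protocol 7.3), Days 8 and 15 follow 15 mg, Days 22 and 29 follow 30 mg, and Days 36 and 43 follow 45 mg; all have 1-week look-backs. The 25 scheduled 60 mg visits to Month 60 comprise 2 of 1 week, 2 of 2, 3 of 4, 1 of 15.13 and 17 of 13.04. The mean is (2 + 4 + 12 + 15.13 + 221.7)/25 = 10.2 weeks. Participants with a dose reduction would add some longer look-backs at lower doses.

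**6. Person-time rate.** Dividing the percentages in step 2 by the time covered gives 1.99 to 2.00 per 100 person-years at every visit type, so the artefact goes when episodes are short. With 4-week episodes the rate over-corrects: 0.191 × 52.18 = 10.0 per 100 person-years at weekly visits against 0.651 × 4 = 2.6 at quarterly ones.

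**The case against.** The strongest reply is that these are descriptive tables. No trend test or comparison among post-baseline visits is planned, and the endpoint is change from baseline. Adverse events are collected and summarized independently, and C-SSRS responses are listed. The any-time ideation shift (Table 14.3.4.7.3) does not depend on how follow-up is cut into visits. Exclusion criterion 10 removes people with recent suicidal behavior, more serious ideation or judged current risk, so counts may be very small: at 0.5 per 100 person-years, 0.07 expected at a weekly visit and 0.94 at a quarterly one, of 750.

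Much of this stands and limits the size of the point. It does not make the figures comparable. The any-time table covers ideation only. SAP 8.4.6 also mentions any-time incidence when it assigns doses, but no display for behavior or self-injury is named.

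A reader might go further in three ways that the documents do not support:
- **That suicidality must appear to rise with time on drug.** The schedule produces steps at Weeks 10 and 16 and at Month 9, a slight fall at Month 12, then a flat line. Persistence shrinks the steps, and loss of susceptible participants can reverse them.
- **That EOS always looks falsely low.** That holds only against quarterly visits. For someone who stops in the weekly phase, 11 days is longer than 7.
- **That by-visit percentages should be replaced by pooled blocks.** Protocol 13.7.7 calls for by-visit summaries, and a Weeks 1 to 12 block would mix all four dose levels.

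**Conclusion.** The point holds as one of comparability. The look-back runs from about 1 week to about 15 weeks, and the planned percentages and shift categories ignore it, so they cannot be compared across visits. On the planned titration the by-dose columns confound dose with look-back.

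With constant risk and short episodes, quarterly and Month 9 values are about 13 and 15 times the weekly ones. With mean episodes of 4 to 52 weeks the quarterly ratio is about 3.4 to 1.2, and attrition could offset it. The look-backs follow from the documents; every event rate, episode length and attrition pattern is an assumption. The primary endpoint is untouched, but the correction is cheap enough that the SAP should include it.

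**What to change.** - Keep Tables 14.3.4.7.1 and 14.3.4.7.2 by visit, as Protocol 13.7.7 requires, and footnote the nominal look-back at each visit.
- Add to SAP 8.4.6 the number of participants with a Yes per person-time covered by the forms, from actual visit dates, for ideation, behavior and self-injury. Present it overall and by dose, with the EOT-to-EOS period beside the on-treatment rate. State how a form whose look-back spans a dose change is assigned; the SAP's existing rule, the dose received before the evaluation, could serve.
- Add an any-time post-baseline incidence display for suicidal behavior and self-injury, alongside the planned ideation shift.

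The rate should supplement the percentages and not stand alone, because it over-corrects when ideation persists across visits. The cost is SAP wording and one or two extra descriptive tables with sparse counts. No new data are needed.

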8.4.7. Physician Withdrawal Checklist (PWC-20)

The PWC-20 is a shorter version of the Penn Physician Withdrawal Checklist based on the 20 items that provided the best differentiation from placebo in previous trials. The PWC-20

is made up of a list of 20 symptoms (eg, loss of appetite, nausea-vomiting, diarrhea, anxiety-nervousness, irritability) that are rated on a scale of 0 (not present) to 3 (severe) ([Rickels 2008](#)). The PWC-20 will be used to monitor for the presence of potential withdrawal syndrome following discontinuation of SAGE-324.

Summarization of PWC-20 data will be presented using the Safety Set – overall and by dose last received immediately prior to the evaluation. Descriptive statistics for the total PWC-20 score will be presented at End of Treatment (defined as the first available assessment after the last dose of study within 1 day of last dose) and End of Study. The change from End of Treatment to End of Study in PWC-20 total score will be provided. The number and percentage of participants with each PWC-20 item and reporting severe on a PWC-20 item will be presented at each visit. Descriptive statistics for the number of PWC-20 items and the number of severe PWC-20 items experienced at each visit will also be presented.

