8.4.2. End of Study Activities

The duration of participation in this study is dictated by the duration of continued administration of IP. If the IP is permanently discontinued, two further study visits will be conducted: one approximately 3 days after IP discontinuation (EOT Visit) and another approximately 14 days after IP discontinuation (EOS Visit). If the participant does not attend the EOS Visit, they will be considered to be lost to follow-up.

If the participant withdraws consent for disclosure of future information, the sponsor will retain and continue to use any data collected before such a withdrawal of consent.

If a participant withdraws from the study, he/she may request destruction of any samples taken and not tested, and the investigator must document this in the site study records.

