5. STUDY DESIGN

5.1. Overall Design

This study is an open-label study to evaluate the long-term safety and tolerability of SAGE-324 in participants with Essential Tremor (ET) who have completed the planned End of Treatment (EOT) Visit and who were not early terminated during the planned Treatment Period in another SAGE-324 study. This study includes a Screening Period of up to 28 days, a Treatment Period with weekly outpatient visits for the first 8 weeks, outpatient visits on Weeks 10, 12, 16, 20, and 24, and quarterly outpatient visits thereafter to the end of dosing, and a 14-day Follow-up Period. See the Schedule of Assessments ([Appendix A](#)) for the full list of study assessments and timings. The study is schematically presented in [Figure 1](#).

Participants who have provided informed consent will undergo screening assessments up to 28 days prior to the planned day of dosing. Eligible participants will complete additional eligibility and baseline assessments.

[figure not shown]
Starting on Day 1, participants will self-administer on an outpatient basis a single dose of SAGE-324 once daily in the evening before bed, with a snack if bedtime is not within 2 hours of the evening meal. The dosing will start at 15 mg, and according to the dose escalation schedule provided in Figure 1 below, will be escalated to 60 mg starting on Day 43. If a participant experiences adverse events (AE) at any time during the Treatment Period that are considered by the investigator to be related to the investigational product (IP) and not tolerable, the investigator may reduce the dose of IP in 15 mg decrements, including during the initial dose escalation period. Administration of IP will be interrupted for 3 to 8 days before the initiation of the reduced dose.

During the Treatment Period, participants will return to the study center for safety, tolerability [REDACTED] as specified in [Appendix A](#). In addition, safety phone call study visits will be conducted as deemed appropriate by the investigator to review the current status of the participant. Participants will be trained in the use of software applications and devices necessary to complete questionnaires and/or self-rated study assessments.

The Treatment Period will continue for as long as the participant continues to self-administer SAGE-324 or until marketing authorization, projected to be up to approximately 5 years.

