Follow-up visits will be conducted on an outpatient basis when participants have completed the Treatment Period. Participants will continue to complete questionnaires as indicated in [Appendix A](#) and will return to the clinic 3 (± 3) days after the last dose of SAGE-324 for safety, tolerability [REDACTED] at the End of Treatment (EOT) Visit.

Participants will return to the study center for an End of Study (EOS) Visit, 14 (± 3) days after the last dose of SAGE-324.

Figure 1: Study Design

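### SAP 8.4.7 accepts a PWC-20 End of Treatment total only within 1 day of the last dose, although the EOT visit is set for day 3 (±3), so 5 of its 7 permitted days fail

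*SAP*

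**What the plan says.** SAP 8.4.7 plans descriptive statistics for the PWC-20 total at two time points, EOT and EOS. It gives EOT its own definition in parentheses: "defined as the first available assessment after the last dose of study within 1 day of last dose". The same section adds a within-participant comparison: "The change from End of Treatment to End of Study in PWC-20 total score will be provided". Item results are handled separately: "The number and percentage of participants with each PWC-20 item and reporting severe on a PWC-20 item will be presented at each visit".

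The visit schedule is stated consistently elsewhere. SAP 5.1 says that participants "will return to the clinic 3 (± 3) days after the last dose of SAGE-324" for the EOT visit. The column headings of protocol Table 4 read "EOT 3 (± 3) days after last dose of SAGE-324" and "EOS 14 (± 3) days after last dose of SAGE-324", and protocol 8.4.2 also puts the EOT visit at about 3 days after discontinuation. Table 4 marks the PWC-20 only in those two columns, and protocol Tables 2 and 3 have no PWC-20 row. SAP 5.1 describes dosing as "a single dose of SAGE-324 once daily in the evening before bed".

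SAP 4.2 names PWC-20 responses and total score as a secondary endpoint. Protocol 13.7.8 leaves the details of the PWC-20 analysis to the SAP.

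**The concern.** The analysis definition and the visit schedule do not fit together. A participant who attends the EOT visit on its target day has no PWC-20 assessment that meets the SAP's definition of EOT, and no other scheduled PWC-20 can stand in for it.

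Two summaries depend on the definition: the EOT total and the change from EOT to EOS. The PWC-20 is not measured before or during treatment, so that change is the only within-participant comparison planned for the scale. Protocol 13.2 rules out imputation, so an excluded EOT total stays missing and takes the change score with it.

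The item and severe-item counts are given by visit and carry no such limit. Appendix C lists a single PWC-20 table (14.3.4.8), so its EOT totals and its EOT item counts could rest on different participants.

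**Working it through.** The plan states no figure to reproduce here. The check is a count of whole days since the last dose.

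**Inputs**
- EOT visit: target day 3, window ±3 (SAP 5.1; protocol 7.1 and Table 4).
- EOS visit: target day 14, window ±3 (same places).
- Scheduled PWC-20 assessments: EOT and EOS only (protocol Table 4).
- SAP limit for the EOT total: after the last dose and no more than 1 day from it (SAP 8.4.7).
- Dosing: once daily, in the evening (SAP 5.1).

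**Permitted EOT days.** 3 − 3 = 0 to 3 + 3 = 6, that is {0, 1, 2, 3, 4, 5, 6}, 7 days.

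**Days that meet the limit, lenient reading.** {0, 1}: 2/7 = 28.6%. Days that fail: {2, 3, 4, 5, 6}, 5/7 = 71.4%. Target day 3 is among them.

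**If a day-0 clinic visit precedes the evening dose.** That assessment is not after the last dose. If day 0 is still counted as a permitted day, only day 1 passes, so 1/7 = 14.3% pass and 6/7 = 85.7% fail. If day 0 is instead removed from the permitted days as well, 5/6 = 83.3% fail.

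**Could the EOS assessment qualify?** EOS days are 14 − 3 = 11 to 14 + 3 = 17. None is within 1 day of the last dose.

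**Interval covered by the change score**, both visits in window:
- EOT taken at the nominal visit: 11 − 6 = 5 to 17 − 0 = 17 days (to 17 − 1 = 16 if day 0 is before the dose); target 14 − 3 = 11.
- EOT limited to days 0 and 1: 11 − 1 = 10 to 17 − 0 = 17 days.

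The 1-day limit therefore gives a narrower interval, but only by discarding most of the permitted visit days.

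**The case against.** The strongest reply is that the loss may never occur. SAP 8.4 says that safety endpoints are summarized by nominal visit and refers to Section 8.3.2, which is not visible, for choosing a record. A programmer following that general rule would use the EOT visit whatever its day. This does not settle the matter. Section 8.4.7 gives its own explicit definition for this score, and the visible text cites 8.3.2 only for choosing among several values. At best the SAP then holds two conflicting rules.

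The limit may also be deliberate. With no pre-dose PWC-20, an assessment close to the last dose could have been meant as the reference for EOS, and SAP 8.4.3 uses a similar 1-day limit for the last on-treatment ECG value. The intent cannot be determined from the documents. If it was deliberate, the visit schedule does not support it.

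A third point concerns the remedy. Without a day cutoff, a late EOT visit would be pooled with timely ones. For example, protocol 7.4 allows an interruption of 3 to 8 days before a reduced dose, and a participant who then stops for good may already be past day 6. This is a fair caution, and it is why days since last dose should be reported. A limit at the scheduled window, days 0 to 6, would also remove the contradiction, but it would again exclude assessments from late visits.

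It is also true that the study is descriptive, that the table's n would reveal a shortfall, and that SAP Table 4 keeps the raw values in listings. These points limit the severity but do not remove the contradiction.

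**Conclusion.** The concern holds. As written, the definition excludes on-schedule PWC-20 assessments on 5 of the 7 permitted EOT days, including the target day. The count is 6 of 7 if day 0 precedes the evening dose, or 5 of 6 if day 0 is dropped altogether; the conclusion is the same on each count.

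It rests on two readings: that the specific definition in 8.4.7 prevails over the general nominal-visit rule, and that the non-visible Section 8.3.2 does no more than the visible text says. It assumes nothing about when participants actually attend, so neither the share of participants lost nor the direction of any bias can be given.

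The effect is on the tabulation of part of a named secondary endpoint, and no data are lost. It should be fixed before the tables are produced.

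**What to change.** In SAP 8.4.7, delete the 1-day limit and define EOT for the PWC-20 as the assessment recorded at the nominal EOT visit after the last dose, in line with SAP 8.4 and with no further day cutoff. In Table 14.3.4.8, show n and a summary of days since last dose for the EOT total, and footnote the EOT-to-EOS change as a comparison of two post-dose time points. If a value within 1 day of the last dose is also wanted, present it as a separate summary with its own n.

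The cost is one SAP sentence, one footnote and one table line. No new data and no protocol amendment are needed, and clinical management does not change. The small downside is that EOT scores will span more days since the last dose, which the added line makes visible.
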